4.6.2. Description of investigational medicinal product

The investigational drug is ranibizumab (Lucentis®) and will be prescribed by the investigator for treatment of diabetic macular edema. Ranibizumab is approved for intravitreal injection in wet age related macula degeneration, diabetic macular edema, retinal vein occlusions and choroidal neovascularization in pathologic myopia.

Ranibizumab (Lucentis®) binds to the receptor binding site of active forms of VEGF-A, including the biologically active, cleaved form of this molecule, VEGF₁₁₀. VEGF-A has been shown to cause neovascularization and leakage in models of ocular angiogenesis. The binding of ranibizumab to VEGF-A prevents the interaction of VEGF-A with its receptors (VEGFR1 and VEGFR2) on the surface of endothelial cells, reducing endothelial cell proliferation, vascular leakage, and new blood vessel formation. The most common adverse events following intra-ocular injection are conjunctival hyperemia and subconjunctival hemorrhage. Serious adverse events related to the injection procedure have occurred in < 0.1% of intravitreal injections, including endophthalmitis, rhegmatogenous retinal detachments, and iatrogenic traumatic cataracts (Heier 2006).

4.6.2.1. Manufacture of the investigational medicinal product

The drug supplied for this study will be manufactured by Novartis.

4.6.2.2. Supply and labelling of investigational medicinal product

Drug will be supplied to the investigator as commercially available Lucentis® by the site's pharmacy after prescription. No trial specific labelling will take place.

4.6.2.3. Storage of investigational medicinal product

The trial medication will be kept at the respective hospital pharmacies that are responsible for storage of the medication in accordance to applicable laws and local standards. The IMP should be stored in a secure, limited-access location according to the summary of product characteristics (2°-8°C, protected from light, freezing must be avoided). IMP will be delivered to the site on demand according to local practice.

4.6.3. Dispensing of investigational medicinal product

The local investigator or his/her designee will document dispensed IMP for each subject. Destruction of IMPs will be performed by the trial sites/pharmacies and will be documented according to local practice.

4.6.4. Assignment of trial subjects to treatment groups

Randomization will be done by using a randomly computer generated list allocating a patient number to each of the two investigational arms in a 1:1 ratio.

4.6.5. Selection of dosage of investigational medicinal product

See 4.6.1

4.6.6. Time of administration and adjustments to dosage of the investigational medicinal product in the individual trial subject

No dosage adjustments are planned in this clinical trial. See 4.6.1 for administration details.

4.6.7. Blinding, Unblinding

Observer-masking (assessment of BCVA, macular thickness, capillary drop-out) is done to guard against detection bias. Unblinding procedures are not applicable (treatment is not blinded).

4.6.8. Previous and concomitant medication

Permitted concomitant therapies include cataract surgery. Other surgical therapies, e.g. vitrectomy, are not permitted during the study and will be considered treatment failure.

Similarly, other pharmacological treatments for macular edema, e.g. triamcinolone or other steroids or other anti-VEGF drugs (local or systemic) are not permitted during the study period.

Any therapy (except medications which are excluded by the trial's exclusion criteria) is allowed for treatment of the underlying disease diabetes mellitus.

Concomitant therapy will be documented on the appropriate trial database/CRF pages.

4.6.8.1. Rescue therapy for emergencies

Rescue medication allowed in this study is panretinal and/or focal laser treatment (after 3 consecutive monthly injections) and only if a significant progression of neovascularization with associated threat of visual loss is seen. Laser treatment will be documented on the appropriate trial database/CRF pages.

The ranibizumab injection can be performed at the same day as a laser therapy, but not earlier than 30 minutes after laser treatment.

If the therapeutic effect will be considered insufficient by either the patient or the treating physician the patient may be withdrawn from the study and is able to receive whatever treatment is considered to be necessary.

4.6.9. Continuation of treatment after the end of the clinical trial

The investigator must provide follow-up medical care for all patients who are prematurely withdrawn from the study, or must refer them for appropriate ongoing care.

4.7. Efficacy and safety variables

4.7.1. Measurement of efficacy and safety variables

4.7.1.1. Primary target variable

- Change of best corrected visual acuity in ETDRS letters score at month 12 when compared with baseline (measured by the difference in ETDRS letters score between month 12 and baseline according to internal guideline of Charité Department of Ophthalmology)

4.7.1.2. Secondary target variables

- Number of treatments with Ranibizumab up to 6, 12, 18 and 24 months of treatment respectively
- Mean average change in BCVA at 6, 12, 18 and 24 months after initial treatment
- Macular thickness (as measured with OCT) at 6, 12, 18, and 24 months after initial treatment
- Time to reach target HbA1c
- Number of neovascular complications: need for panretinal laser photocoagulation (PRP)
- Rates of ocular and of systemic AEs (retinal detachment, Central retinal artery occlusion, endophthalmitis; and rates of stroke, myocardial infarction, severe hypoglycemia)

4.7.2. Fundus photography

At the initial time point (screening visit) and months 12 and 24, digital colour fundus photos should be made of the central area and every quadrant; central, nasal, nasal-superior, superior, temporal-superior, temporal, temporal-inferior, inferior, nasal-inferior (a total of nine photos, with an optional overview photo (compilation of the nine photos)). At the other visits that require fundus photographs as indicated in the visit schedule, digital fundus photos of the central area and the optic nerve head alone will be acquired.

4.7.3. Optical Coherence Tomography (OCT)

A Spectral Domain OCT of Heidelberg Engineering (Spectralis, Heidelberg Engineering, Heidelberg, Germany) should be used to perform the measurements at every time point indicated in the visit schedule. OCT macular volume scans of both eyes should be performed.

4.7.4. Fluorescein Angiography

Standardized angiography is performed by fluorescein angiography using a confocal scanning laser ophthalmoscope (Spectralis, Heidelberg Engineering). Besides central images of the macula, the periphery will be covered with ultra-wide lens using 9 separate images. The angiograms follow a standardised protocol.

Fluorescein angiograms will include pre-injection reflectance images using the green illumination (514 nm) and autofluorescence images using the blue (488 nm) illumination. Angiographic images will be taken within the first second after dye inflow, and thereafter in 1 second intervals for 15 seconds, then at 30 seconds, 60 seconds, 120 seconds, 300 seconds, and 600 seconds, after injection. For all central images, the 30° mode and the 512x512 resolution will be used. Subsequently, peripheral images are taken with 102° lens in total 9 fields.

4.7.4.1. Description of visits

Screening assessments should be performed 1 to 7 days before treatment start (Visit 1).

Table 2: Investigations during the clinical trial (until month 12)

Visits	Screenig	1	2	3	4	5	6	7	8	9	10	11	12
Month	-1 to -7 days	1	2	3	4	5	6	7	8	9	10	11	12
Procedure	a time frame of ± 1 week is allowed until visit 12												
Inclusion/exclusion criteria	x												
Demographic data & med. history	x												
Informed consent ¹	x												
Pregnancy status ²	x												
Randomization	x												
Study treatment		x	x	x	x ⁵	x ⁵	x ⁵	x ⁵	x ⁵	x ⁵	x ⁵	x ⁵	x ⁵
Clinical lab tests ³	x			x			x			x			x
Blood glucose and blood pressure measurement (group 1) (regular diabetic control) ⁴	x			x			x			x			x
Blood glucose and blood pressure measurement (group 2) (intensive diabetic control)	x	x	x	x	x	x	x	x	x	x	x	x	x
Funduscopy	x			x	x	x	x	x	x	x	x	x	x
BCVA (ETDRS)	x	x	x	x	x	x	x	x	x	x	x	x	x
Slitlamp	x	x	x	x	x	x	x	x	x	x	x	x	x
Fluorescein angiography	x						x						x
Fundus photography	x			x			x			x			x
OCT	x	x	x	x	x	x	x	x	x	x	x	x	x
Concomitant medication	x	x	x	x	x	x	x	x	x	x	x	x	x
AE/SAE (documentation & report)		x	x	x	x	x	x	x	x	x	x	x	x
SCR = Screening, to be performed within one week before study treatment start ¹ written informed consent has to be obtained before any study related investigations are performed ² for women of child-bearing potential a test will be performed at screening; all other women will be asked for pregnancy status. In the course of the trial women of child-bearing potential will be asked for pregnancy status before Ranibizumab treatment or fluorescein angiography ³ triglycerides, HbA1c ⁴ group 1 patients will be cared for diabetes by their general practitioner and will visit the site additionally every three months as indicated ⁵ checkup visit according to local practice & possible PRN therapy													

Table 3: Investigations during the clinical trial (months 12-24: follow-up time)

Visits/Months	13	14	15	16	17	18	19	20	21	22	23	24
Procedure	a time frame of ± 4 weeks is allowed until visit 24											
Ranibizumab treatment ¹	according to local practice & possible PRN therapy											
Clinical lab tests			X			X			X			X
Blood glucose and blood pressure measurement (group 1) (regular diabetic control)			X			X			X			X
Blood glucose and blood pressure measurement (group 2) (intensive diabetic control)			X			X			X			X
Funduscopy			X			X			X			X
BCVA (ETDRS)	X	X	X	X	X	X	X	X	X	X	X	X
Slitlamp	X	X	X	X	X	X	X	X	X	X	X	X
Fluorescein angiography ¹						X						X
Fundus photography			X			X			X			X
OCT	X	X	X	X	X	X	X	X	X	X	X	X
Concomitant medication	X	X	X	X	X	X	X	X	X	X	X	X
AE/SAE documentation/reporting ²	X	X	X	X	X	X	X	X	X	X	X	X
¹ women of child-bearing potential will be asked for pregnancy status before each ranibizumab treatment or fluorescein angiography ² until 30 days after the patient has stopped the ranibizumab treatment												

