4.6.1. Treatments to be given

In all patients (in both study arms) the diabetic macular edema will be treated with intravitreally given ranibizumab.

Dosage and administration of Ranibizumab

Injections are administered according to the current summary of product characteristics Lucentis®, i.e. monthly until maximum BCVA can be observed:

Starting at visit 1, ranibizumab will be administered intravitreally in a multiple-dose regimen of 0.5 mg of ranibizumab every month for a total of 3 injections and as a PRN treatment thereafter (subsequent injections until maximum BCVA is observed).

Injection is discontinued when

- no BCVA improvement in spite of treatment is seen after the first three injections (i.e. after three consecutive monthly visits)

BCVA assessments will take place monthly. Monthly injections are resumed when

- decrease in BCVA due to worsening of DME in the opinion of the investigator is observed

Injections are continued until BCVA improvement is seen after three consecutive monthly visits.

If a subject is unable to receive study drug because of medical or personal reasons, treatment should be resumed within 2 weeks of the scheduled treatment. If a subject is unable to receive study drug within 2 weeks of the scheduled treatment, the subject will be allowed to miss the scheduled dose and resume treatment at the next regularly scheduled time. Dosing should not occur more frequently than every 4 weeks. Missed doses will not be replaced.

Ranibizumab Injection

Procedures will be implemented to minimise the risk of potential adverse events associated with serial intraocular injections (e.g., endophthalmitis). Aseptic technique must be observed by clinic staff involved in the injection tray assembly, anesthetic preparation and administration, and study drug preparation and administration. In addition to the procedures outlined in the protocol, added safety measures in adherence to specific institutional policies associated with intraocular injections should be observed.

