4.7.5. Rationale for assessment procedures

Macular edema is assessed both anatomically (OCT and fluorescein angiography) and functionally (BCVA). For assessment of the glycemic status of the patients, blood glucose measurements and other laboratory tests are required.

The intervals for clinical assessment in the current trial were set to 4 weeks based on the Lucentis® SmPC's recommendations for visual acuity assessments.

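### Visit 1 is the first injection but is labelled month 1, so the secondary BCVA and macular-thickness readings fall at least one month before their stated times, and no visit is nominally at 24 months

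*Combined protocol and SAP*

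**What the plan says.** Section 4.7.4.1: "Screening assessments should be performed 1 to 7 days before treatment start (Visit 1". Section 4.6.1: "Starting at visit 1, ranibizumab will be administered intravitreally in a multiple-dose regimen". Visit 1 is therefore both the start of treatment and the first injection.

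Table 2 has a screening column at 1 to 7 days before treatment, followed directly by Visit 1 as month 1 and so on to Visit 12 as month 12. Table 3, headed "Investigations during the clinical trial (months 12-24: follow-up time", continues with the same number for visit and month up to 24. The visit window is 1 week either side up to Visit 12. In year 2 a deviation of 4 "weeks is allowed until visit 24".

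Section 4.7.1.2 defines a secondary endpoint as "Mean average change in BCVA at 6, 12, 18 and 24 months after initial treatment". Macular thickness has the same four times and the same origin. The synopsis and section 2.3 agree.

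The primary endpoint (sections 4.7.1.1 and 6.1.3) is the change from baseline at month 12, with no stated origin. Section 6.2 bases the sample size on the standard deviation of the change over 12 months.

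The visit interval is described in two ways. Section 4.6.1 says "BCVA assessments will take place monthly". Section 4.7.5 says "The intervals for clinical assessment in the current trial were set to 4 weeks".

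**The concern.** If the first injection is time zero, a visit numbered v lies v − 1 intervals after it, not v. Every secondary BCVA and thickness reading taken at the visit bearing the endpoint's month number is then early. The result reported for 24 months would refer to a time the nominal schedule does not reach.

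Two other gaps make this harder to settle at analysis. Monthly and 4-weekly spacing differ by nearly two months by Visit 24. BCVA is measured at both screening and Visit 1, and the plan does not say which of them is baseline.

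What is at stake is the time to which each estimate refers and the length of exposure to intensified control when it is measured.

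**Working it through.** **Elapsed time.** Inputs: Visit 1 is the first injection (sections 4.6.1 and 4.7.4.1); spacing is either a calendar month (365.25 / 12 = 30.44 days) or 28 days (section 4.7.5). Formula: time since first injection = (v − 1) × interval.

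| Visit and label | Calendar months | 4-weekly, days | 4-weekly, months |
|---|---|---|---|
| 6 | 5 | 5 × 28 = 140 | 4.6 |
| 12 | 11 | 11 × 28 = 308 | 10.1 |
| 18 | 17 | 17 × 28 = 476 | 15.6 |
| 24 | 23 | 23 × 28 = 644 | 21.2 |

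**Visit windows** (applied to each nominal date, not cumulated).
- Visit 12, ±7 days: 10.77 to 11.23 months (calendar) or 9.89 to 10.35 (4-weekly). Counting from screening at day −7 and adding the full late window gives 11 + 14/30.44 = 11.46 months, still short of 12.
- Visit 24, ±28 days: 22.08 to 23.92 months (calendar) or 20.24 to 22.08 (4-weekly). The latest calendar date is 23 × 30.44 + 28 = 728 days, against 24 × 30.44 = 730.5 days. Counting from screening at day −7 would give 24.15 months, but the endpoint is counted from initial treatment.

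**Visits that do fall at the stated times.** On calendar spacing, Visits 7, 13 and 19 lie at 6, 12 and 18 months, with BCVA and OCT, under other labels. Twenty-four months would need a Visit 25, which is not scheduled. On 4-weekly spacing the visit nearest 12 months is Visit 14 (13 × 28 = 364 days, 11.96 months), and 24 months would need a Visit 27 (26 × 28 = 728 days, 23.92 months).

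**Year-2 windows.** A tolerance of 28 days equals the 4-weekly interval and is 28/30.44 = 92% of a calendar month. The permitted ranges of neighbouring visits overlap, so a value dated near month 18 may belong to more than one visit.

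**Power.** Section 6.2 assumes a difference of 2.0 letters, SD 3.5, two-sided 5% and 56 per arm. Noncentrality = δ / (3.5 × √(2/56)), with 110 degrees of freedom and critical value 1.98.
- Plan's figure: δ = 2.0, noncentrality 3.02, power 85%. It reproduces.
- Linear growth to 2.0 at 12 months (assumption): at 11 months δ = 2.0 × 11/12 = 1.83, noncentrality 2.77, power 78%. At 44 weeks δ = 2.0 × 10.12/12 = 1.69, noncentrality 2.55, power 71%.
- Levelling off (assumption): δ(t) = 2.0 × (1 − e^(−t/τ)) / (1 − e^(−12/τ)). With τ = 3 months, δ is 1.99 at 11 months and 1.97 at 44 weeks, power 84% at both. With τ = 6 months, δ is 1.94 and 1.88, power 83% and 81%.
- Plateau before the reading (assumption): power stays at 85%.

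**The case against.** The strongest reply is that the primary endpoint is not contradicted. It says only month 12, and Table 2 labels Visit 12 as month 12, so the two agree on their face. The assumed 2.0 letters can be read as the difference at that visit as planned. This stands. A reader might infer that the primary analysis is mis-timed and that the trial has 71% to 78% power. The documents do not support that: they give no effect trajectory, and those figures need both linear growth and a 12-month origin for the 2.0 letters. What remains for the primary is an undefined origin and baseline visit, although the 12-month basis of the SD in section 6.2 and the 12-month treatment period in the synopsis suggest elapsed time.

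A second reply is that the 4-week interval appears in a rationale section, while the operative text and the table row speak of months. The time plan leaves exactly 24 months between the last patient's first and last visits. This makes a labelling slip on calendar spacing more plausible than follow-up ending near 21 months. It does not remove the discrepancy, which is one month even on calendar spacing.

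A reader might also infer that nothing is measured at 6, 12 or 18 months. On calendar spacing Visits 7, 13 and 19 are at those times; only 24 months has no nominal visit.

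The closest-measurement rule in section 6.1.3 does not help, because it applies only when the month 12 score is missing.

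**Conclusion.** The schedule and the secondary BCVA and macular-thickness endpoints contradict each other. Visits bearing the endpoint month numbers are one month early at all four times on calendar spacing. On 4-weekly spacing they are early by 1.4 months at month 6, rising to 2.8 months at month 24. Counted from first injection, Visit 24 reaches 23.9 months at most. This rests only on Visit 1 being the first injection, which the protocol states twice.

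For the primary endpoint the finding is an ambiguity of origin and baseline, not a contradiction. A reader might take the shift as a source of bias between arms. It is not, because both arms follow the same BCVA and OCT schedule. Any loss of power lies between none and 14 percentage points (85% to 71%) over the trajectories tried, and nothing in the documents says where in that range. The point should be corrected because stated times are wrong as written and the correction is cheap, not because the comparison is invalid.

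**What to change.** 1. Reconcile the monthly wording of section 4.6.1 with the 4 weeks of section 4.7.5, and state one interval.
2. State the time origin for month 12, and say whether screening or Visit 1 supplies the baseline BCVA.
3. Then take one of two routes. Either label Visit 1 as month 0 (day 0), so that the whole month-12 and month-24 assessments, with their laboratory tests and imaging and the ±1 week window at month 12, fall 12 and 24 calendar months after first injection. Or keep the schedule and restate the endpoint times as 5, 11, 17 and 23 months (at months 12 and 24: 44 and 92 weeks if 4-weekly).
4. Define non-overlapping analysis windows for year 2, for example half the visit interval either side.

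Relabelling is sufficient only on calendar spacing. On 28-day spacing it gives 12 × 28 = 336 days (11.04 months) and 24 × 28 = 672 days (22.08 months). Simply reading the primary endpoint from the present Visit 13 is not free: that visit has a ±4 week window, no laboratory tests, fundus photography or angiography, and lies in the phase when Group 2 is seen every 3 months.

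Cost: with relabelling, the final assessment moves about one month later, within the 24 months of the time plan, and one monthly check is added; its clinical content is for the sponsor to settle. With restated times, the declared follow-up becomes slightly shorter. The rest is wording and window definitions, best fixed before the data are analysed.

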4.7.5. Rationale for assessment procedures

Macular edema is assessed both anatomically (OCT and fluorescein angiography) and functionally (BCVA). For assessment of the glycemic status of the patients, blood glucose measurements and other laboratory tests are required.

The intervals for clinical assessment in the current trial were set to 4 weeks based on the Lucentis® SmPC's recommendations for visual acuity assessments.

4.7.6. Pharmacokinetics/Determination of drug levels

Not applicable.

4.8. Data quality assurance

4.8.1. Monitoring

The trial sites will be monitored to ensure the quality of the data collected. The objectives of the monitoring procedures are to ensure that the trial subject's safety and rights as a study participant are respected, that accurate, valid and complete data are collected, and that the trial is conducted in accordance with the trial protocol, the principles of GCP and local legislation.

All investigators agree that the monitor regularly visits the trial site and assure that the monitors will receive appropriate support in their activities at the trial site. The declaration of informed consent (see Section 5.4) includes a statement to the effect that the monitor has the right – while observing the provisions of data protection legislation – to compare the data entered in the trial database, respectively with the trial subject's medical records (doctor's notes, laboratory printouts etc.). The investigator will secure access for the monitor to all necessary documentation for trial-related monitoring. The aims of the monitoring visits are as follows:

- To check the declarations of informed consent
- To monitor trial subject safety (occurrence and documentation/reporting of AEs and SAEs)
- To check the completeness and accuracy of entries in the trial database
- To validate the entries in the trial database against those in the source documents (source data verification, SDV),
- To perform drug accountability checks
- To evaluate the progress of the trial
- To evaluate compliance with the trial protocol
- To assess whether the trial is being performed according to GCP at the trial site
- To discuss with the investigator aspects of trial conduct and any deficiencies found

A monitoring visit report is prepared for each visit describing the progress of the clinical trial and any problems.

The exact extent of the monitoring procedures is described in a separate monitoring plan.

